10 SUPPORTING DOCUMENTATION AND OPERATIONAL CONSIDERATIONS

10.1 Regulatory, Ethical, and Study Oversight Considerations

10.1.1 Informed Consent Process

10.1.1.1 Consent/Assent and Other Informational Documents Provided To Participants

Consent forms describing in detail the study intervention, study procedures, and risks are given to the participant and written documentation of informed consent is required prior to starting intervention/administering study intervention.

10.1.1.2 Consent Procedures and Documentation

Informed consent is a process that is initiated prior to the individual's agreeing to participate in the study and continues throughout the individual's study participation. Consent forms will be IRB-approved and the participant will be asked to read and review the document. The investigator will explain the research study to the participant and answer any questions that may arise. A verbal explanation will be provided in terms suited to the participant's comprehension of the purposes, procedures, and potential risks of the study and of their rights as research participants. Participants will have the opportunity to carefully review the written consent form and ask questions prior to signing. The participants should have the opportunity to discuss the study with their family or surrogates or think about it prior to agreeing to participate. The participant will sign the informed consent document prior to any procedures being done specifically for the study. Participants must be informed that participation is voluntary and that they may withdraw from the study at any time, without prejudice. A copy of the informed consent document will be given to the participants for their records. The informed consent process will be conducted and documented in the source document (including the date and time), and the form signed, before the participant undergoes any study-specific procedures. The rights and welfare of the participants will be protected by emphasizing to them that the quality of their medical care will not be adversely affected if they decline to participate in this study.

10.1.2 Study Discontinuation and Closure

This study may be temporarily suspended or prematurely terminated by the Sponsor or the PI at any site if there is sufficient reasonable cause. Written notification, documenting the reason for study suspension or termination, will be provided by the suspending or terminating party to study participants, investigator, funding agency, the Investigational New Drug (IND) Sponsor and regulatory authorities. If the study is prematurely terminated or suspended, the Principal Investigator (PI) will promptly inform study participants, the IRB, and Sponsor and will provide the reason(s) for the termination or suspension. Study participants will be contacted, as applicable, and be informed of changes to study visit schedule.

Circumstances that may warrant termination or suspension include, but are not limited to:

- Determination of unexpected, significant, or unacceptable risk to participants
- Demonstration of efficacy that would warrant stopping
- Insufficient compliance to protocol requirements
- Data that are not sufficiently complete and/or evaluable
- Determination that the primary endpoint has been met
- Determination of futility

Study may resume once concerns about safety, protocol compliance, and data quality are addressed, and satisfy the Sponsor, IRB and/or Food and Drug Administration (FDA).

In terminating the study, the Sponsor and the Principal Investigator will assure that adequate consideration is given to the protection of the subjects' interests.

10.1.3 Confidentiality and Privacy

Participant confidentiality and privacy is strictly held in trust by the participating investigators, their staff, and the Sponsor and their interventions. This confidentiality is extended to cover testing of biological samples and genetic tests in addition to the clinical information relating to participants. Therefore, the study protocol, documentation, data, and all other information generated will be held in strict confidence. No information concerning the study or the data will be released to any unauthorized third party without prior written approval of the Sponsor.

All research activities will be conducted in as private a setting as possible.

Information about study subjects will be kept confidential and managed according to the requirements of the Health Insurance Portability and Accountability Act of 1996 (HIPAA).

The study monitor, other authorized representatives of the Sponsor, representatives of the IRB, regulatory agencies or pharmaceutical company supplying study product may inspect all documents and records required to be maintained by the investigator, including but not limited to, medical records (office, clinic, or hospital) and pharmacy records for the participants in this study. The clinical study site will permit access to such records.

The study participant's contact information will be securely stored at the clinical site for internal use during the study. At the end of the study, all records will continue to be kept in a secure location for as long a period as dictated by the reviewing IRB, Institutional policies, or Sponsor requirements.

10.1.4 Future Use of Stored Specimens and Data

Data collected for this study will be analyzed and stored at the University of Pennsylvania. After the study is completed, the de-identified data will be stored for future use by other researchers with IRB approval to do so. Biological specimens (stool samples) will be preserved in frozen storage for future analysis utilizing the same guidelines.

10.1.5 Safety Oversight

Safety oversight will be under the direction of a Data and Safety Monitoring Board (DSMB) composed of individuals with the appropriate expertise. Members of the DSMB should be independent from the study conduct and free of conflict of interest, or measures should be in place to minimize perceived conflict of interest. The DSMB will meet at least semiannually to assess safety and efficacy data of the study. The DMSB will operate under the rules of an approved charter that will be written and reviewed at the organizational meeting of the DSMB.

10.1.6 Clinical Monitoring

A monitoring plan that satisfies the International Council on Harmonisation (ICH) Good Clinical Practices (GCP) guidelines for clinical monitoring will be used. The investigator will allocate adequate time for such monitoring activities. The Investigator will also ensure that the monitor or other compliance or quality assurance reviewer is given access to all study-related documents and study related facilities (e.g. pharmacy, diagnostic laboratory, etc.), and has adequate space to conduct the monitoring visit. The monitor, a member of the Women's Health Clinical Research Center, will lead this effort, and report findings to the PI and the DSMB when necessary. The monitor will have full knowledge of the study protocol, Manuals of Procedures, and is familiar with the database system, REDCap (Research Electronic Data Capture) and is trained to review patient charts. The monitor along with the Project Manager/Lead Study Coordinator at the site will be responsible for training and supervising other personnel.

10.1.7 Quality Assurance and Quality Control

During monitoring visits, the monitor will review CRFs to ensure data accuracy, completeness, and clarity, including laboratory reports and other subject records with the stipulation that subject confidentiality will be strictly maintained in accordance with local and federal regulations, including HIPAA requirements. Instances of missing or uninterruptible data will be resolved in coordination with the Investigator.

10.1.8 Data Handling and Record Keeping

10.1.8.1 Data Collection and Management Responsibilities

Data will be collected prospectively by designated research personnel at the study site, supervised by the PI. Original source documents will be kept in the study subject folder. Well-designed data collection forms (CRFs) will be developed to minimize data collection and

recording errors. CRFs will be completed, with copies and will be printed and stored in binders in a secure location to which only study personnel will have access. Subject diaries will also be collected and stored in a secure location. Subjects will be assigned a unique study identification number, and PHI will be kept separately with a master file stored on a secure, passwordprotected computer. Linkage to PHI will be stored until study analysis and publication completion, and then will be destroyed. Administrative forms will be designed, such as visit procedure checklists, to assist the research staff in complying with protocol procedures. All data are being collected solely for the purpose of research and do not become part of the subject's medical record.

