2.3 Risk/Benefit Assessment

2.3.1 Known Potential Risks

The main risks of this study are related to administration of the investigational product. The most severe possible risks include allergic reaction, donor-derived infection, aspiration, and death. Other risks include nausea, vomiting, abdominal pain, diarrhea, flatulence, and fever.

As noted above, potential risks of the FMT treatment for FI includes gastrointestinal symptoms (including fever, aspiration, belching, bloating, nausea or vomiting, gastroesophageal reflux, abdominal cramps, abdominal pain, diarrhea, constipation). This is the first attempt to administer FMT for FI in women, however the risks are not expected to be significantly different from that reported in the literature.

Theoretical long-term risks may include: changes in metabolism, weight changes, development of autoimmune conditions.

Other risks include loss of privacy or confidentiality, as a result of study staff interacting with subjects.

These risks will be discussed with subjects during the informed consent process. The eligibility criteria will help mitigate these risks (e.g., excluding subjects with neutropenia or bowel perforation, and not permitting subjects at risk for aspiration to receive investigational product via upper gastrointestinal delivery). To minimize the risk of privacy and confidentiality loss, the minimum number of required study staff will interact with subjects, and all collected data will be protected as above.

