5.3 Lifestyle Considerations

After administration of the investigational product (PMT-002) there is no way for investigators to stop or retrieve the product from the subject. Additionally, it is unknown how long the product will remain in the subject's body; thus, subjects should be fully informed that withdraw of the investigational product is not possible and be comfortable with this information prior to administration. Furthermore, as this is a first in human trial for the indication of FI unforeseen side effects are expected.

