10.1.8.2 Study Records Retention

Data (electronic and paper) will be stored in a secure location until study analysis and publication completion, after which any linkage to PHI will be destroyed. Anonymized microbial nucleic acid sequence data and associated metadata will be uploaded on public databases (i.e., the National Center for Biotechnology Information's Sequence Read Archive) as required by funding agencies. Final records will be retained per institutional guidelines.

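### The protocol orders the link between study number and identity destroyed after publication and names no product-to-participant key to be kept, so tracing a donor product to the woman who received it would be lost

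*Combined protocol and SAP*

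**What the plan says.** Destruction of the link is stated twice. Section 10.1.8.1 reads "Linkage to PHI will be stored until study analysis and publication completion, and then will be destroyed". Section 10.1.8.2 says data are stored "until study analysis and publication completion, after which any linkage to PHI will be destroyed". Section 10.1.8.1 adds that study data "do not become part of the subject's medical record".

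Section 10.1.3 points the other way on records in general: "At the end of the study, all records will continue to be kept in a secure location", for a period set by the IRB, the institution or the sponsor. Section 10.1.8.2 also sends final records to institutional retention rules without giving a period.

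On the product, section 5.3 says "there is no way for investigators to stop or retrieve the product from the subject" and "it is unknown how long the product will remain in the subject's body". Section 2.3.1 says "The most severe possible risks include allergic reaction, donor-derived infection, aspiration, and death" and, separately, "Theoretical long-term risks may include: changes in metabolism, weight changes, development of autoimmune conditions". Section 8.3.8 makes suspected donor-to-patient infection, and a rise in long-term events, grounds for a study-wide pause. Section 10.1.4 keeps stool frozen for later analysis. The last planned contact is at 180 days (section 8.1.6).

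**The concern.** The plan foresees harms that could surface late and could be tied to a particular donor, yet it orders the removal of the record that connects a donor product to a named woman. Two questions would then have no documented route to an answer. If something is learned about a donor after the link is gone, which women received that donor's material? If a woman reports a late harm, which product did she receive, and which sequence data are hers? The first bears on who should be told and followed. The second bears on whether a late event can be attributed at all. Planned safety contact stops at 180 days, so later information would depend wholly on what records remain and whether they can be joined.

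**Working it through.** There is no figure in the plan to reproduce, and the point rests on no alpha, power, rate or sample size. The check is a comparison of sections, plus one illustration of timing.

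**1. What is destroyed.** Section 10.1.8.1 describes a master file holding identities apart from study numbers and orders the linkage destroyed. Section 10.1.8.2 is wider, since it covers any linkage. Neither section exempts a product or donor key.

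**2. What might survive.**
- Section 10.1.3: all records are kept after study end. It does not say whether they still identify women. Contact details are described as held for use while the study runs.
- Section 10.1.1.2: signed consent forms exist. The text does not name them among the retained records, but it does not exclude them.
- Section 6.2.1: a product accountability log, a label check and notice of the visit date to the manufacturing facility. The text does not say that any of these records donor, product and participant together. If one did carry identity, the wording of 10.1.8.2 could reach it too.
- Medical chart: 10.1.8.1 keeps study data out of it. A chest x-ray is done at the treatment visit (8.1.2) and contact attempts may be noted in the medical record (7.2), so the chart may show that something took place. Nothing says it would show which product was given.

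**3. Which tasks each set of records supports.**

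| Task | Records that may be kept under 10.1.3 | Needs a product-to-participant key |
|---|---|---|
| Warn all treated women as a group | Possible, if names or consents are retained | No |
| Identify the women who received a given donor's product | Not shown | Yes |
| Match a woman's late harm to her product or sequence data | Not shown | Yes |

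The second and third rows are what the destruction sentences remove. They do not depend on a product being shared between recipients: a single woman and a single donor are enough.

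**4. When.** The trigger is completion of analysis and publication. Section 10.1.8.3 requires the study report within 12 months of data lock, but makes a manuscript depend on the importance of the results and sets no deadline for it. As an illustration, assume data lock at the last woman's 180-day contact (about 6 months after her dose) and publication 0 to 12 months after lock. The earliest point is 6 + 0 = 6 months after the last dose. At the 12-month end it is 6 + 12 = 18 months. It could be later, or never occur if no manuscript is written.

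**5. Do the sections conflict?** Section 10.1.3 speaks of all records and 10.1.8.1 and 10.1.8.2 of the linkage. A master file linking number to person is naturally read as a study record, so staff would face two rules for one file. A reading that separates records from linkage is also possible. The text does not settle it.

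**The case against.** A reader might infer that the women become untraceable and could never be warned. The documents do not support that. Destroying a link is not destroying identities. Section 10.1.3 keeps all records, 10.1.8.2 retains final records, source documents sit in a participant folder (10.1.8.1), and consents are signed. With about 15 women at one centre, a group warning may well be feasible without any study-number key. Nor can it be said that the master file is the only link, because the contents of the accountability log are not described.

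Further points on the other side are fair. De-linking after publication is a deliberate privacy choice. Sections 10.1.3 and 10.1.8.2 can be read as compatible. The protocol does not describe lots shared between recipients. Consent pages were removed before review, and manufacturing and donor-screening documents are not supplied, so look-back terms could sit there. Donor testing before release (6.2.2), the pause rule (8.3.8) and follow-up of serious events to resolution (8.3.6) give some protection.

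All of this limits the claim but does not remove it. A group warning does not show who received the product in question, and it does not help to attribute a late harm. Testing before release cannot cover what becomes known afterwards, and adverse event reporting closes at 180 days. De-identified sharing (10.1.4, 10.1.8.2) does not require that a separately secured key be destroyed. The protocol states an explicit rule to destroy, so the point is more than missing detail.

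**Conclusion.** The concern holds in a limited form. As written, sections 10.1.8.1 and 10.1.8.2 end participant-level tracing between donor product and woman at an undated point, with no stated substitute, although the protocol itself recognises an irretrievable product of unknown persistence, donor-derived infection and long-term harms. It would apply to every treated woman. The probability of needing the key cannot be estimated from the documents.

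The conclusion assumes that the linkage wording covers any product key that identifies a woman, and that no document outside this text preserves one. If the accountability log or manufacturing records are kept and identify recipients, the loss is smaller and the remaining task is to say so. This is a matter of safety traceability and record-keeping that should be corrected because the remedy is cheap. It does not touch the endpoints, the sample size or the analysis.

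**What to change.** Reconcile sections 10.1.3, 10.1.8.1 and 10.1.8.2 by replacing the two destruction sentences. Suggested text:

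*A key holding study number, identity and the PMT-002 product and donor identifier is stored separately from study data, encrypted, by [named role], for the retention period set by the IRB, the institution and the sponsor under section 10.1.3. It is opened only for safety tracing. Data sets that are shared or made public remain de-identified.*

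State in section 6.2.1 that the accountability log records the product identifier against the study number, so that the key can be completed. State the retention of the key, and the possibility of re-contact for safety reasons, in the consent form.

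The cost is an amendment to a few sentences in the protocol and consent form, and one locked file. The downside is a small residual confidentiality risk from holding identities longer, which separate storage, encryption and the existing safeguards in 10.1.3 are meant to contain.

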10.1.8.2 Study Records Retention

Data (electronic and paper) will be stored in a secure location until study analysis and publication completion, after which any linkage to PHI will be destroyed. Anonymized microbial nucleic acid sequence data and associated metadata will be uploaded on public databases (i.e., the National Center for Biotechnology Information's Sequence Read Archive) as required by funding agencies. Final records will be retained per institutional guidelines.

10.1.8.3 Publication Plan

The investigator is responsible for authoring a final clinical study report and sharing with the Sponsor team. The Clinical Study Report will be issued within 12 months of data lock and the results summary will be posted to clinicaltrials.gov. as required by legal agreement, local law, or regulation. A manuscript will be progressed for publication in the scientific literature if the results provide important scientific or medical knowledge.

10.1.9 Protocol Exceptions and Deviations

10.1.9.1 Exception (Prospective action)

An *exception* is defined as a one-time, intentional action or process that departs from the approved study protocol, intended for one occurrence. If the action disrupts the study progress, such that the study design or outcomes may be compromised, or the action compromises the safety and/or welfare of study subjects, advance documented approval from the Regulatory Sponsor and local regulatory review committees, per institutional guidelines, is required. Approval from the Regulatory Sponsor must be received prior to submission to the local regulatory review committees.

10.1.9.2 Deviation (Retrospective action)

A *deviation* is defined as a one-time, unintentional action or process that departs from the approved study protocol, involving one incident and identified retrospectively. If the deviation disrupts study progress, such that the study design or outcomes may be compromised, or the deviation compromises the safety and/or welfare of study subjects, the deviation must be

reported to the Regulatory Sponsor within 24 – 48 hours of PI knowledge and to local regulatory review committees per institutional guidelines.

The PI and the study team should document all scenarios where the protocol is not followed and provide, in particular:

- Who deviated from the protocol;
- What was the deviation;
- When did the deviation occur;
- How did the deviation happen;
- What is the impact of the deviation;
- A root cause analysis of why the deviation occurred.

If the assessment is determined to be of limited impact (minor deviation), the documentation for this assessment and the outcome should be reported to the Sponsor at the time of annual report. Reporting to the IRB should follow specific local requirements.

If the assessment results in a determination that any of the following are potentially affected, the deviation would be considered of significant impact:

- having the potential to adversely affect subject safety; OR
- increases risks to participants; OR
- adversely affects the integrity of the data; OR
- violates the rights and welfare of participants; OR
- affects the subject's willingness to participate in research;
- there is a potential for an overall impact on the research that should be shared with the IRB for consideration and development of next best steps to address it.

Report the following information on the Sponsor's exception/deviation form:

- Protocol number;
- Subject number;
- Description of the exception or deviation;

- Impact on subject safety;
- Impact on data integrity.

Deviations that are assessed by the PI to not disrupt the study progress, such as not affecting the study design or outcome, or compromising the safety and/or welfare of study subjects, should be documented in site records and contain documentation of the PI's assessment.

These scenarios should be reported to the Sponsor within 24 - 48 hours of discovery. Reporting to IRB should follow local requirements.

